#### 12.1.6 Reference Safety Information (RSI)

A list of medical events that defines which reactions are expected for the IMP within a given trial and thus determining which Serious Adverse Reactions (SARs) require expedited reporting.

The RSI is contained in a clearly identified section of the Summary of Product Characteristics (SmPC)

**For this trial the Reference Safety Information is:** section 4.8 – Undesirable effects, of the Flynn Pharma Ltd, Phenytoin Sodium Flynn Hard Capsules 300mg SmPC and the Zentiva Levetiracetam 750mg Film-Coated Tablets SmPC. The applicable SmPC version will be the latest version that has been approved by the MHRA for use in this trial.

## 12.2 Expected Adverse Reactions/Serious Adverse Reactions (AR /SARs)

All expected Adverse Reactions are listed in the latest MHRA approved version of the RSI as specified in section 12.1.6. This must be used when making a determination as to the expectedness of the adverse reaction. If the adverse reaction meets the criteria for seriousness, this must be reported as per section 12.5

## 12.3 Expected Adverse Events/Serious Adverse Events (AE/SAE)

#### Expected SAEs exempt from expedited reporting

Due to the nature of traumatic brain injury, affected individuals can often develop surgical and medical complications. Expected systemic or surgical complications associated with TBI will not be reported as SAEs However, all SAEs (both reportable or non-reportable) will be captured on the study CRF (Case Report Form) or SAE recording log in the Investigator Site File, so that all serious adverse event data is captured.

In addition, any of the following systemic SAEs are also exempt from expedited reporting:

#### Pulmonary

- Pneumonia
- Pneumothorax
- Atelectasis
- Aspiration
- Pleural effusion/empyema
- Ventilator-related complications
- Adult respiratory distress syndrome
- Need for prolonged mechanical or positive pressure airway ventilation

## Cardiac

- Angina
- Pericardial effusion
- Pericarditis

## Renal

- Urinary tract infection
- Urinary retention
- Haematuria
- Renal dysfunction
- Renal failure maybe requiring full renal support

## **Thrombotic**

- Deep vein thrombosis
- Pulmonary embolism
- Mesenteric thrombosis
- Other thromboses (e.g. limb)

#### **Hepatobiliary**

- Pancreatitis
- Liver failure

#### Bowel

- Infective diarrhoea or colitis (e.g. Clostridium difficile)
- Diarrhoea of other causes
- Bowel ischaemia
- Ileus

#### Wound other than craniotomy or craniectomy

- Infection
- Dehiscence

#### Other miscellaneous general complications

- Decubitus ulcer
- Other infections (e.g. MRSA)
- Anaesthetic-related complication
- Coagulopathy
- Pyrexia
- Septicaemia

#### 12.4 Evaluation of adverse events

The Sponsor expects that adverse events are recorded from the point of Informed Consent regardless of whether a participant has yet received a medicinal product. Individual adverse events should be evaluated by the investigator. This includes the evaluation of its seriousness, and any relationship between the investigational medicinal product(s) and/or concomitant therapy and the adverse event (causality).

## 12.4.1 Assessment of seriousness

Seriousness is assessed against the criteria in section 12.1.4. This defines whether the event is an adverse event, serious adverse event or a serious adverse reaction

#### 12.4.2 Assessment of causality

Definitely: A causal relationship is clinically/biologically certain. This is therefore an Adverse Reaction

- Probably: A causal relationship is clinically / biologically highly plausible and there is a plausible time sequence between onset of the AE and administration of the investigational medicinal product and there is a reasonable response on withdrawal. This is therefore an Adverse Reaction.
- Possible: A causal relationship is clinically / biologically plausible and there is a plausible time sequence between onset of the AE and administration of the investigational medicinal product. This is therefore an Adverse Reaction.
- Unlikely: A causal relation is improbable and another documented cause of the AE is most plausible. This is therefore an Adverse Event.
- Unrelated: A causal relationship can be definitely excluded and another documented cause of the AE is most plausible. This is therefore an Adverse Event.

Unlikely and Unrelated causalities are considered NOT to be trial drug related Definitely, Probably and Possible causalities are considered to be trial drug related

A pre-existing condition must not be recorded as an AE or reported as an SAE unless the condition worsens during the trial and meets the criteria for reporting or recording in the appropriate section of the CRF.

- 12.4.3 Clinical assessment of severity
- Mild: The participant is aware of the event or symptom, but the event or symptom is easily tolerated
- Moderate: The participant experiences sufficient discomfort to interfere with or reduce his or her usual level of activity
- Severe: Significant impairment of functioning; the subject is unable to carry out usual activities and / or the participant's life is at risk from the event.

#### 12.4.4 Recording of adverse events

Adverse events and adverse reactions should be recorded in the medical notes and the appropriate section of the CRF and/or AE/AR log. Serious Adverse Events and Serious Adverse Reactions should be reported to the sponsor as detailed in section 12.5.

#### 12.5 Reporting Serious Adverse Events

Each Principal Investigator needs to record all adverse events of special interest and report serious adverse events to the Chief Investigator using the trial specific SAE form within 24 hours of their awareness of the event.

The Chief Investigator is responsible for ensuring the assessment of all SAEs for expectedness and relatedness is completed and the onward notification of all reportable SAEs to the Sponsor immediately but not more than 24 hours of first notification. The sponsor has to keep detailed records of all SAEs reported to them by the trial team.

The Chief Investigator is also responsible for prompt reporting of all reportable serious adverse event findings to the competent authority (e.g. MHRA) of each concerned Member State if they could:

- adversely affect the health of participants
- impact on the conduct of the trial
- alter the risk to benefit ratio of the trial
- alter the competent authority's authorisation to continue the trial in accordance with Directive 2001/20/EC

The completed SAE form can be emailed. Details of where to report the SAEs can be found on the MAST SAE form and the front cover of the protocol.

### 12.6 Reporting of Suspected Unexpected Serious Adverse Reactions (SUSARs)

All suspected adverse reactions related to an investigational medicinal product (the tested IMP and comparators) which occur in the concerned trial, and that are both unexpected and serious (SUSARs) are subject to expedited reporting. Please see section 12.1.6 for the Reference Safety Information to be used in this trial.

#### 12.6.1 Who should report and whom to report to?

The Sponsor delegates the responsibility of notification of SUSARs to the Chief Investigator. The Chief Investigator must report all the relevant safety information previously described, to the:

- Sponsor
- competent authorities in the concerned member states (eg MHRA)
- Ethics Committee in the concerned member states

The Chief Investigator shall inform all investigators concerned of relevant information about SUSARs that could adversely affect the safety of participants.

#### 12.6.2 When to report?

#### 12.6.2.1 Fatal or life-threatening SUSARs

All parties listed in 12.5.1 must be notified as soon as possible but no later than **7 calendar days** after the trial team and Sponsor has first knowledge of the minimum criteria for expedited reporting.

In each case relevant follow-up information should be sought and a report completed as soon as possible. It should be communicated to all parties within an additional **8 calendar days**.

#### 12.6.2.2 Non-fatal and non-life-threatening SUSARs

All other SUSARs and safety issues must be reported to all parties listed in 12.5.1 as soon as possible but no later than 15 calendar days after first knowledge of the minimum criteria for expedited reporting. Further relevant follow-up information should be given as soon as possible.

#### 12.6.3 How to report?

#### 12.6.3.1 Minimum criteria for initial expedited reporting of SUSARs

Information on the final description and evaluation of an adverse reaction report may not be available within the required time frames for reporting. For regulatory purposes, initial expedited reports should be submitted within the time limits as soon as the minimum following criteria are met:

a) a suspected investigational medicinal product

b) an identifiable participant (e.g. trial participant code number)

c) an adverse event assessed as serious and unexpected, and for which there is a reasonable suspected causal relationship

d) an identifiable reporting source

and, when available and applicable:

- an unique clinical trial identification (EudraCT number or in case of non- European Community trials the sponsor's trial protocol code number)

- an unique case identification (i.e. sponsor's case identification number)

### 12.6.3.2 Follow-up reports of SUSARs

In case of incomplete information at the time of initial reporting, all the appropriate information for an adequate analysis of causality should be actively sought from the reporter or other available sources. Further available relevant information should be reported as follow-up reports.

In certain cases, it may be appropriate to conduct follow-up of the long-term outcome of a particular reaction.

#### 12.6.3.3 Format of the SUSARs reports

Electronic reporting is the expected method for expedited reporting of SUSARs to the competent authority. The format and content as defined by the competent authority should be adhered to.

## 12.7 Pregnancy Reporting

All pregnancies reported in trial participants during the treatment phase of the trial and for 1 month post treatment should be reported to the Chief Investigator and the Sponsor using the relevant Pregnancy Reporting Form within 24 hours of notification.

Pregnancy is not considered an AE unless a negative or consequential outcome is recorded for the mother or child/fetus. If the outcome meets the serious criteria, this would be considered an SAE.

## 13 Toxicity – Emergency Procedures

In the event of suspected occurrences of major toxicity, the trial drug will be withdrawn.

#### 14 Evaluation of Results (Definitions and response/evaluation of outcome measures)

All data will be presented to the Data Monitoring Committee, who will meet on a regular basis throughout the trial. The DMC will then prepare a report for the Trial Steering Committee who will provide overall supervision of the trial.

#### 14.1 Response criteria

#### 14.1.1 Mortality

This will be measured from the date of randomisation to the 24 month follow up and will be reported for all deaths due to all causes. The cause of death is to be recorded if known.

#### 14.1.2 Quality of life

Quality of life will be assessed by means of the EQ-5D-5L questionnaire to generate quality adjusted life years.

#### 14.1.3 PTS recurrence

PTS recurrence will be measured from the date of randomisation to the 24 month follow up and will be reported for all causes.

#### 15 Storage and Analysis of Samples

Urine pregnancy test samples will be analysed at point of care and then discarded. These will be the same point of care tests used during normal clinical practice. No further samples will be collected or stored as part of this trial.

## 16 Statistics

### 16.1 Statistical methods

The main statistical analysis will be performed on an intention-to-treat basis, which will include all randomly assigned participants.

The primary endpoint (occurrence of PTS) is binary (yes / no). The primary analysis will estimate the absolute difference between the active treatment groups and control in terms of the incidence of PTS using logistic regression with an additive link, adjusting for baseline covariates (subdural haematoma (yes / no), number of lobes with a contusion (none / one / two / more than two), craniotomy or craniectomy (yes / no), depressed skull fracture (yes / no), initial severity of injury GCS 3-8 / 9-15, intradural lesion (yes / no) and will furnish the estimates with 95% confidence intervals. MAST DURATION will use a standard 2-sided p-value compared to a 5% significance level; MAST-PROPHYLAXIS will adjust for multiple testing using Dunnett's test at an overall 5% significance level stipulating that the smaller of the 2-sided p-values must be less than 2.7% to achieve statistical significance. A direct comparison between active arms (phenytoin vs levetiracetam) in MAST-PROPHYLAXIS will be a secondary analysis. The baseline covariates will be those used to stratify the randomisation: depressed skull fracture (yes / no), intradural lesion (yes / no) and initial severity of injury (GCS 3-8, GCS 9-15). Site will be handled as a random effect as there are anticipated to be 29 sites.

Sensitivity analyses will be performed to assess the influence of missing data and deviations from the intention-to-treat principle.

The GOSE will be analysed with an ordinal method adjusting for baseline covariates. Further secondary endpoints will be summarized using appropriate techniques according to whether the variable is binary, categorical, continuous or time-to-event. Categorical and binary variables will be summarized using bar charts, frequency tables and comparisons made using logistic regression.

Continuous variables will be summarized, broken down by treatment arm, using Box plots, mean, median, SD, max, min and compared using linear regression. Time-to-event variables will be summarized using Kaplan-Meier plots, and compared using the log-rank test. Predefined subgroups for exploratory analyses will be: subdural haematoma (yes / no), number of lobes with a contusion (none / one / two / more than two), craniotomy or craniectomy (yes / no), depressed skull fracture (yes / no), initial severity of injury GCS 3-8 / 9-15, intradural lesion16.1 (yes / no), lesion site (temporal, insular, frontal, parietal, occipital, basal ganglia, thalamo-capsular, posterior fossa) and lesion type (extradural hematoma, acute subdural haematoma, contusion, chronic subdural haematoma, diffuse axonal injury, skull vault fracture, other). A detailed statistical analysis plan will be prepared by the study statistician without reference to the unblinded data.

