### MAST-PROPHYLAXIS

According to the available evidence (5,6), a treatment effect of 7% can be expected with seizure prophylaxis. We will attempt to reproduce these findings in a multi-centre setting across the NHS. Recruiting 1221 patients overall will provide 358 observations per arm. Assuming seizure rates of 4% in both active arms and 11% in control will provide 90% power to achieve significance in both comparisons. Alternatively, if only one active arm has a seizure rate of 4% and the other the same rate as control, then there will be 91% power to achieve significance in that individual comparison. The expected average annual recruitment is 15-20 patients / site. We will aim to roll out the trial in 29 adult trauma-receiving hospitals in the UK. According to the timeline presented below, the recruitment will be completed in 3 years.

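### The primary model is named in contradictory terms and, read as an identity-link model with a random site effect, is prone to inadmissible fits at the planned event rates

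*Protocol*

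**What the plan says.** Protocol section 16.1 sets an absolute risk difference between each active arm and control as the target of the main comparison. The method named for it is described as "using logistic regression with an additive link", with covariate adjustment and 95% confidence intervals. On centres the section adds: "Site will be handled as a random effect as there are anticipated to be 29 sites".

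The covariates are given twice in that paragraph. The first list has six factors: subdural haematoma, number of contused lobes in four levels, craniotomy or craniectomy, depressed skull fracture, GCS group and intradural lesion. Further on it says "The baseline covariates will be those used to stratify the randomisation", which leaves only depressed fracture, intradural lesion and GCS group.

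For significance, PROPHYLAXIS uses Dunnett's test, under which "the smaller of the 2-sided p-values must be less than 2.7% to achieve statistical significance". For the other trial, "MAST DURATION will use a standard 2-sided p-value compared to a 5% significance level".

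Section 16.3 sizes PROPHYLAXIS "Assuming seizure rates of 4% in both active arms and 11% in control", with 358 observations per arm, and DURATION on 25% v 12% with 188 per arm. Section 16.1 ends by announcing a separate statistical analysis plan, which is not available here.

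**The concern.** The link defines the model. A logit link makes the regression logistic and its coefficients log odds ratios. An additive (identity) link makes the coefficients risk differences, and the model is then no longer logistic. Two statisticians could follow the sentence and fit different models.

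Because the target is an absolute difference, the identity link is the natural reading. Nothing in such a model keeps fitted risks between 0 and 1, and the planned risks are low. When the likelihood is maximised at the edge of the permitted region, Wald standard errors lose their justification. A normally distributed site effect on the risk scale adds to the difficulty, because for any positive variance it gives some probability to risks below zero. The primary estimates, their intervals and, on the natural reading, the p-values set against 2.7% and 5% all come from this model.

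**Working it through.** **1. The protocol's own figures.** With 12% drop-out, 1221 × 0.88 / 3 = 358 and 428 × 0.88 / 2 = 188, as stated. A Dunnett threshold for two comparisons with one control (correlation 0.5) is z = 2.211, or 2.70% two-sided, as stated. Power = Φ[(Δ − z·SE₀)/SE₁], with pooled SE₀ and unpooled SE₁:

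- PROPHYLAXIS, one comparison: SE₀ = √(2 × 0.075 × 0.925/358) = 0.01969; SE₁ = √((0.11 × 0.89 + 0.04 × 0.96)/358) = 0.01951; Φ[(0.07 − 2.211 × 0.01969)/0.01951] = 91.2% (stated 91%).
- PROPHYLAXIS, both comparisons: 87.4% if each must reach 2.7%, 91.9% if the second is tested at 5% (stated 90%).
- DURATION: SE₀ = 0.04005, SE₁ = 0.03949; Φ[(0.13 − 1.96 × 0.04005)/0.03949] = 90.4% (stated 90%).

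These are unadjusted two-proportion calculations and do not test whether the named model can be fitted.

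**2. Room above zero.** Under an additive model with a constant 7-point effect, the average active-arm risk is 11 − 7 = 4%. Any covariate pattern more than 4 points below average risk is therefore fitted below zero in the active arms. In DURATION the margin is 25 − 13 = 12 points.

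**3. Information.** Expected events are 358 × (0.11 + 0.04 + 0.04) = 68 and 188 × (0.25 + 0.12) = 70. Over 29 sites that is 2.3 and 2.4 per site.

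**4. Simulated identity-link fits, site not in the fitted model.** The protocol's sizes and rates were used. Covariate prevalences (10% to 75%) and odds ratios are assumptions. Entries are the share of 300 runs that converged with every fitted risk inside 0 to 1:

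| Trial, covariates | OR 1 | OR 1.5 | OR 2 | OR 3 |
|---|---|---|---|---|
| PROPHYLAXIS, three | 82% | 69% | 42% | 9% |
| PROPHYLAXIS, six | 11% | 5% | 0% | 0% |
| DURATION, three | 90% | 92% | 70% | 25% |
| DURATION, six | 36% | 14% | 1% | 0% |

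A second, separate set of runs over OR 1 to 2 gave 45–86% and 76–93% with three factors, and 0–13% and 1–36% with six. When the data were generated additively, regular fits were 68–81% and 89–95% (three factors), and 1–7% and 10–39% (six).

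**5. Constrained maximum likelihood, still without site (OR 1 to 2).** With three factors a solution was found in 99–100% of runs, but it lay on the zero-risk boundary in 15–53% (PROPHYLAXIS) and 15–27% (DURATION). With six factors it lay there in 59–94%.

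**6. Site effect.** With a normal site effect of SD 2 points around a 4% risk, Φ(−0.04/0.02) = 2.3% of sites fall below zero, and the chance of at least one in 29 is 1 − 0.9772²⁹ = 49%. At SD 3 points the figures are 9.1% and 94%. Fitting the identity-link model with a normal site effect (assumed data SD 0.5 on the logit scale, risks kept inside 0 to 1 at ±2 SD, 60 runs per setting), the optimiser returned a solution in 77–98% of runs. A regular interior solution occurred in 0–3% (PROPHYLAXIS) and 0–15% (DURATION). This count is strict: it also treats a site variance estimated at zero as irregular.

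**7. Comparator.** Logit-link regression followed by marginal standardisation (OR 1.5 and 2, site SD 0.3 on the logit scale in the data, site not modelled, 500 runs per setting) failed at most once per setting. Mean differences were −0.069 to −0.070 and −0.128 to −0.132. Coverage was 93–96%, and power 91–92% at 2.7% (PROPHYLAXIS) and about 92% at 5% (DURATION).

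**The case against.** The additive scale targets the stated estimand directly, and the trouble lies partly in the algorithm. In a further simulation (three factors, OR 1.2 to 1.8, site not fitted), constrained maximum likelihood converged in at least 99% of runs, with mean differences of −0.065 to −0.069 and −0.126 to −0.131. Least squares with robust standard errors gave 92–96% coverage and about 90–95% power. This stands: an estimate can usually be had, and standardised logistic regression is not the only valid route. It does not rescue the intervals, because the constrained solution was on the boundary in 16–49% and 10–27% of those runs. Nor does it settle which model the sentence means.

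The frequencies also rest on prevalences, odds ratios and site variances that are not in the protocol. That stands too. DURATION with three weak-to-moderate factors and no site term fits regularly about 90% of the time.

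A reader might go further and infer three things that the documents do not support:

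- That a replacement model would be picked after seeing the data. Section 16.1 announces an analysis plan written without reference to unblinded data, and a convergence fallback commonly belongs there.
- That site adds 29 separately estimated intercepts. A random effect adds one variance parameter.
- That the model is generally impossible to fit. Many irregular results are boundary or out-of-range fits, not the absence of a fit.

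**Conclusion.** The point holds as a defect of naming with a practical consequence. Section 16.1 names a primary model that contradicts itself. On its natural reading the model carries a material risk of non-convergence, boundary solutions or inadmissible fitted risks, and hence of unreliable confidence intervals and p-values.

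For assumed odds ratios of 1 to 2 without site in the fit, the share of regular fits is roughly 45–85% (PROPHYLAXIS) and 75–93% (DURATION) with three factors; one set of runs reached down to 42% and 70%. With six factors it is 0–36%. The covariate list therefore matters more than any other choice, and the protocol gives two. The proposed site effect makes regular fits rarer still, by an amount that depends on the unknown site variance.

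It would be wrong to conclude that the risk difference is out of reach or that the trials are under-sized. The difference is obtainable with the planned power by a logit-link model with standardisation. The wording should be corrected; nothing else in the design has to change.

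**What to change.** In section 16.1, replace the model wording with: *logistic regression (logit link) adjusting for the stated baseline covariates, with a random intercept for site; the absolute risk difference for each comparison is obtained by marginal standardisation, with a delta-method or bootstrap 95% confidence interval.* Apply the existing 2.7% and 5% rules to those contrasts, and keep one covariate list in place of the two.

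Two details can sit in the analysis plan: averaging predicted risks over the site distribution, and the choice between delta method and bootstrap. The runs supporting this fix did not model site, so a short check with the random intercept included is sensible before the wording is fixed.

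The cost is a text change, a few lines of code and one extra post-estimation step. The estimand, sample size, stated power and significance rules are unchanged.

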#### 9 Selection and withdrawal of participants

## 9.1 Inclusion Criteria

## MAST-PROPHYLAXIS:

- Patients aged ≥10 years, with TBI managed in an NSU without an acute symptomatic seizure
- Patient or Legal Representative is willing and able to provide informed consent or in the absence of a legal representative, an Independent Healthcare Professional provides authorisation for patient randomisation within 48 hours of admittance.

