## MAST-DURATION

Patients who fulfil the eligibility criteria will be randomly assigned to a maximum of 3 months OR a minumum of 6 months duration of a clinically prescribed AED (phenytoin or levetiracetam, choice of drug at clinician's/site's local option). The distribution between trial populations will be 1:1 (<3 months:>6months). In the event of a seizure occurring within the trial period, treatment will continue as per local clinical guidelines regardless of the treatment arm. If treatment management changes within the trial period, patients will remain in the trial.

A secure electronic system will be used for the randomisation of suitable patients. Suitably trained staff will access the secure site and enter the patient details. 24-hour telephone support will be provided for randomisation and eligibility criteria by Trial Investigators or suitable trained delegated persons. Allocation will be stratified by depressed skull fracture (yes / no), intradural lesion (yes / no) and initial severity of injury (GCS 3-8, GCS 9-15).

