# 11.4 Screening & Baseline Assessments

All patients will have a medical history taken and a clinical examination as part of the routine standard care. The following are to be recorded in part 1 of the case report form (CRF):

- Inclusion/exclusion criteria review
- Informed consent process followed and consent or authorisation for enrolment
- Obtained
- Urine pregnancy test (if applicable) for females of child bearing potential
- Routine review of clinical laboratory results
- ECG (if indicated by local policy)
- Standard of Care:
  - Patient medical history (including co-morbidities and relevant medications)
  - Patient demography
  - Injury related events date of TBI, date of PTS, date of possible intubation, date of AED
  - Neurological status
  - o Imaging review

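### Age is in neither covariate list in section 16.1, so the GOSE analysis forgoes some power that data already collected would give

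*Protocol*

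**What the plan says.** Section 16.1 of the Protocol gives the covariates twice in its paragraph on the primary endpoint. The first list has six items: subdural haematoma, number of contused lobes, and "craniotomy or craniectomy (yes / no), depressed skull fracture (yes / no), initial severity of injury GCS 3-8 / 9-15, intradural lesion (yes / no"). Later in the same paragraph: "The baseline covariates will be those used to stratify the randomisation: depressed skull fracture", followed by intradural lesion and GCS in two bands. These are the three factors in section 9.3: "Allocation will be stratified by depressed skull fracture (yes / no), intradural lesion (yes / no) and initial severity of injury (GCS 3-8, GCS 9-15").

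The GOSE sentence comes after this: "The GOSE will be analysed with an ordinal method adjusting for baseline covariates". It names no list of its own. For the remaining secondary outcomes 16.1 gives generic methods only. Binary and categorical variables are compared by logistic regression, continuous ones are summarised "using Box plots, mean, median, SD, max, min and compared using linear regression", and time-to-event variables are compared by the log-rank test. No covariates are attached to any of these.

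On the data side, section 9.1 admits "Patients aged ≥10 years, with TBI managed in an NSU without an acute symptomatic seizure" to MAST-PROPHYLAXIS. MAST-DURATION has the same lower age limit, and neither trial has an upper one. Section 11.4 lists "Patient demography" and neurological status among the baseline items, and section 17.1 says that date of birth is held.

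**The concern.** Age will vary widely in this population. It is a plausible predictor of function months after a head injury, beyond what lesion type, fracture, surgery and a two-band GCS capture. In a proportional-odds model, omitting a prognostic baseline variable moves the treatment log odds ratio towards zero relative to its standard error, so power is lost although the test stays valid.

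GOSE is one of the outcomes that will show whether any fall in seizures comes with better or worse overall recovery. Section 16.3 sizes both trials on seizures alone. MAST-DURATION is the smaller, with 188 observations per arm. Age is already collected, so the loss is avoidable without new data.

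**Working it through.** **1. Is age in any list that could govern GOSE?**

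| Source | Items | Age? | GCS |
|---|---|---|---|
| 16.1, first list | six factors | no | 3–8 / 9–15 |
| 16.1, second list | three stratification factors | no | 3–8 / 9–15 |
| 9.3, stratification | the same three | no | 3–8 / 9–15 |
| 16.1, GOSE sentence | refers to baseline covariates, no list | – | – |

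The two lists in 16.1 disagree with each other. Whichever is kept, age is absent.

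**2. Do the plan's own figures depend on the covariates?** They reproduce from a comparison of two proportions without any covariate:
- PROPHYLAXIS: 3 × 358 / 0.88 = 1220.5, so 1221.
- DURATION: 2 × 188 / 0.88 = 427.3, so 428.
- Power = Φ{(|p₀ − p₁|√n − z√(2p̄q̄)) / √(p₀q₀ + p₁q₁)}.
- PROPHYLAXIS, 11% v 4%, n = 358, two-sided 2.7% (z ≈ 2.21): (0.07 × 18.92 − 2.21 × 0.3725) / 0.3692 ≈ 1.36, so 91.2% (stated 91%).
- DURATION, 25% v 12%, n = 188, two-sided 5%: (0.13 × 13.71 − 1.96 × 0.5491) / 0.5414 ≈ 1.30, so 90.4% (stated 90%).

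Adding age to the GOSE model therefore alters no stated number. No power or precision is stated for GOSE.

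**3. What is age worth in the GOSE model?** The documents supply only the numbers per arm. The following are assumptions: an eight-level outcome under proportional odds, a treatment odds ratio of 1.4, a GCS-band effect of 1.0 on the log-odds scale, and age at a log odds ratio of 0.3, 0.6 or 0.9 per SD (odds ratio 1.35, 1.82, 2.46).

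As a guide to what these strengths mean, take a 50:50 GCS split. The share of latent variance due to age is then b² / (π²/3 + 0.25 + b²):
- 0.09 / 3.63 = 2.5%
- 0.36 / 3.90 = 9.2%
- 0.81 / 4.35 = 18.6%

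Each simulated trial was analysed with the GCS band alone and with the band plus age. The Wald z grows with √n, so the gain in effective sample size is (mean z with age / mean z without age)² − 1.

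| Setting | age 0.3 | age 0.6 | age 0.9 |
|---|---|---|---|
| 358 per arm, 1,000 trials | 4% | 13% | 28% |
| 358 per arm, equal-sized GOSE categories, 50:50 GCS bands, 1,500 trials | 3% | 13% | 32% |
| 188 per arm, 1,000 trials | 4% | 14% | 30% |

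At 358 per arm the middle case is equivalent to about 0.13 × 358 ≈ 47 more patients per arm. At 188 per arm it is about 0.14 × 188 ≈ 26.

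**4. Outcomes compared by linear regression.** If the added covariate explains a share R² of the residual variance, the standard error is multiplied by √(1 − R²), and the equivalent gain in patients is 1/(1 − R²) − 1. For an assumed R² of 5%, 10%, 15% or 20%, the factor is 0.975, 0.949, 0.922 or 0.894, and the gain is 5.3%, 11.1%, 17.6% or 25.0%. The documents do not say which R² applies to EQ-5D-5L, NSI or the Liverpool profile.

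**The case against.** Both lists stand in the paragraph on the primary endpoint, the GOSE sentence has no list of its own, and 16.1 promises a detailed SAP, which is not at hand. Covariates for a secondary outcome are often settled there. Adjusting for the stratification factors is a standard and valid choice. The size of any gain rests wholly on assumed inputs, and at its low end it is negligible.

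Most of this is fair, and it limits the point. It does not remove it. Section 16.1 says what the baseline covariates will be, and the GOSE sentence uses the same term with no other set named. The natural reading is therefore a set without age, and a SAP that added age would depart from it.

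A reader might infer more than the documents support:
- **That the GOSE estimate is biased.** It is not. Randomisation protects the type I error with or without age. The odds ratios with and without age are different quantities (non-collapsibility), so the one nearer to 1 is not a distorted version of the other. The gain in the ordinal model is in power and does not come from a smaller standard error.
- **That age was left out of the analyses of mortality, NSI, EQ-5D-5L and the Liverpool profile.** No covariates are named for these, so there is no list from which age is missing. Stating adjustment there is an addition.
- **That numeric GCS is equally free.** Sections 9.3 and 16.1 show the band, and 11.4 says only that neurological status is recorded. That the score itself is kept is an inference.

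**Conclusion.** The point holds as an efficiency improvement for GOSE. The covariate set that the Protocol prints has no age, although age varies widely and is already held. Under the stated assumptions the gain from adding it is roughly 3–4% more patients if age is a weak predictor, 13% if moderate and 28–32% if strong. The direction is the same in every setting examined. Where this trial lies in that range cannot be found from the documents, since they give neither the prognostic strength of age nor a GOSE effect size. That GOSE has no power calculation of its own is normal for a secondary outcome and is no defect. The primary analysis, its sample size and its stated power are untouched.

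**What to change.** In section 16.1:
- Add age at randomisation to the GOSE model in both trials, as a continuous term (for example a spline), and keep the stratification factors.
- State the same adjustment for the regression analyses of the other 6–24 month outcomes.
- Use numeric GCS in place of the two bands only if the score itself is recorded.
- Leave the primary seizure model unchanged.
- In the same edit, reconcile the two covariate lists, so that it is clear which factors accompany age.

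The cost is a sentence or two in the Protocol, carried into the SAP. For age it needs no new data and no extra patients. The change should be made without reference to unblinded data, as 16.1 already requires of the SAP.
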